ORR will be calculated as the proportion of evaluable patients that have confirmed CR or PR, as defined according to the 2014 Lugano Classification, exact 95% confidence intervals will be calculated for these estimates. CR rate will be similarly estimated. Response rates will also be evaluated based on number and type of prior therapy(ies). Duration and time to response (DOR and TTR), as well as overall survival (OS) and progression-free survival (PFS) will be estimated using the product-limit method of Kaplan and Meier.

Because of the unique immune-related adverse events (IrAEs) observed with checkpoint inhibitors, we will monitor for “unacceptable toxicity” with this new combination of drugs (defined in [Section 10.2](#)). The expected rate of “unacceptable toxicity” should not be $\geq 33\%$. The early stopping rule for unacceptable toxicity will be assessed after enrollment of 12 patients (total, across cohorts) treated at the RP2D and will be assessed once the 12th patient has completed at least 4 cycles of therapy. If >3 “unacceptable toxicity” events occur in the first 12 patients ($\geq 33\%$) treated (across disease subtypes) at RP2D, or at a rate $\geq 33\%$ thereafter at the quarterly review, accrual will be halted and a full review of these events will be performed by the City of Hope Data Safety Monitoring Committee (DSMC). Patient accrual will not resume until approved by the DSMC to do so. These rules are in addition to the quarterly review of all toxicities submitted to the City of Hope Data Safety Monitoring Committee (DSMC). Patients with ongoing toxicity will be followed until resolution or stability.

Sponsor/Licensee:

Investigator-initiated trial at City of Hope
Supported by Merck, Inc.

Case Report Forms

Medidata Rave EDC®

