4.6.4 Rationale for Additional Patients in Expansion Cohort

Monotherapy with PD-1 blockade does not produce durable remissions in the great majority of patients with R/R HL. Therefore, effective therapies for patients with R/R HL who have prior exposure to PD-1 blockade is a major unmet need. Among the initial 42 patients enrolled onto the study, there were 15 patients with prior exposure to PD-1 blockade and the results were extremely promising with 13 out of 15 patients achieving an objective response. Therefore, we will enroll an additional 10 patients with R/R HL who have prior anti-PD-1/PD-L1 exposure to more adequately explore the safety and anti-tumor activity of pembrolizumab plus vorinostat in this unique population. In addition, to minimize heterogeneity among PD-1/PD-L1 exposed patients (some could be PD1/PD-L1-exposed but still sensitive) we narrowed the eligibility to PD-1/PD-L1 refractory to focus on this particular group of patients where there is a high unmet need.

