10.2 Endpoint Definitions

Overall Response Rate (ORR): Defined as the proportion of patients that have a documented CR or PR at any time during study treatment.

Complete Response (CR) rate: Defined as the proportion of patients that have a documented CR at any time during study treatment.

Duration of Response (DOR): Defined as the time from the first achievement of PR or CR to time of PD. Patients who never achieve PR or CR are excluded. Patient who has not had disease progression/relapse at last follow-up is censored at the time of last follow-up. If a patient receives non-protocol anti-lymphoma treatment prior to disease progression, the patient is censored at the time of non-protocol anti-lymphoma treatment.

Overall Survival: Defined as time from initiation of study therapy to death from any cause. If a patient is alive at the last evaluation time period, survival time is censored at the time of last follow-up.

Progression-Free Survival (PFS): Defined as the time from initiation of study therapy to the first observation of disease relapse/progression or death from any cause, whichever occurs first. If the patient has not progressed relapsed or died, the patient is censored at the time of last follow-up. If a patient receives non-protocol anti-lymphoma treatment prior to disease progression, the patient is censored at the time of non-protocol anti-lymphoma treatment.

Toxicity: Toxicity and adverse events will be recorded using the NCI CTCAE 4.03 scale. Observed toxicities will be summarized by type (organ affected or laboratory determination such as absolute neutrophil count), severity (by NCI CTCAE v4.03 and nadir or maximum values for lab measures), date of onset, duration, reversibility, and attribution.

Unacceptable Toxicity: defined as one of the following AEs that is at least possibly related to study treatment, at any point on study therapy:

- Any Gr 3 or higher IrAE that does not resolve to Gr ≤ 1 within 7 days with the exception of:
 - Grade 3 immune-related hepatitis if ALT or AST $< 8 \times$ ULN or total bilirubin $< 5 \times$ ULN.
 - Grade 3 asymptomatic endocrinopathy.
 - Local inflammatory response to study therapy.
- Any other Gr ≥ 4 AE with the exception of:
 - Non-clinically significant laboratory abnormalities
 - Local inflammatory response to study therapy.
- Any Gr 5 AE.

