11.1.3 Analysis of Anti-tumor Activity

This study will aim to obtain preliminary estimates of the anti-tumor activity of the study combination. ORR will be calculated as the proportion of evaluable patients that have confirmed CR or PR, as defined according to the 2014 Lugano Classification, exact 95% confidence intervals will be calculated for these estimates. Response rates will also be evaluated based on number and type of prior therapy(ies). Time to response, duration of response, as well as progression-free survival and overall survival will be estimated using the product-limit method of Kaplan and Meier.

These efficacy analyses will be performed separately for DLBCL, FL, and HL patients. Any patient treated at the RP2D, including those from the dose-escalation cohort, will be included in efficacy analyses. Patients will be evaluable for efficacy assessment if they received at least one dose of vorinostat and one dose of pembrolizumab and underwent at least one response assessment. Patients will be evaluable for efficacy if they discontinued study therapy prior to the first response assessment because of progression of disease rather than solely because of unacceptable toxicity, withdrawal of consent, or investigator decision. If a patient discontinues study treatment prior to the first response assessment due to progressive disease, the treating physician is encouraged to obtain imaging to confirm progression.

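### Duration of response ends only at PD and censors a responder who dies without it, although PFS in the same section counts that death as an event

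*Combined protocol and SAP*

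**What the plan says.** All the definitions are in Section 10.2.

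- **DOR, event:** "Defined as the time from the first achievement of PR or CR to time of PD". Death is not mentioned.
- **DOR, censoring:** "Patient who has not had disease progression/relapse at last follow-up is censored at the time of last follow-up".
- **PFS, event:** "the first observation of disease relapse/progression or death from any cause, whichever occurs first".
- **PFS, censoring:** "If the patient has not progressed relapsed or died, the patient is censored at the time of last follow-up".
- **Both endpoints** are also censored when a patient starts lymphoma treatment outside the protocol before progressing.

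On the method, Section 11.1.3 says: "Time to response, duration of response, as well as progression-free survival and overall survival will be estimated using the product-limit method". The statistical considerations in Section 1.0 agree: "Duration and time to response (DOR and TTR), as well as overall survival (OS) and progression-free survival (PFS) will be estimated", again by Kaplan-Meier. Neither section names a competing-risk method or a rule for death in response, and no other section adds death to the DOR event.

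**The concern.** Two time-to-event endpoints defined in the same section treat the same death differently. A reader who sets DOR beside PFS would expect both to end at that death.

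The choice of estimator makes this more than a matter of wording. Kaplan-Meier with the death censored assumes that the dead responder had the same future risk of PD as responders still under follow-up. The resulting curve describes time to PD as if nobody could die first. A reader is likely to take it as the time for which patients stay alive and in response.

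DOR is the endpoint that describes durability, and more durable response is part of the rationale for adding vorinostat (Section 4.6.1). A definition that can only lengthen the reported duration when deaths are censored at their own date is therefore worth correcting.

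**Working it through.** **1. What happens to a responder who dies without documented PD**

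| Situation | DOR (10.2) | PFS (10.2) |
|---|---|---|
| Dies, no PD, no outside lymphoma treatment | censored | event |
| Starts outside lymphoma treatment without PD, then dies | censored at that treatment | censored at that treatment |
| PD documented, then dies | event at PD | event at PD |

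The endpoints disagree only in the first row. The DOR text does not state that deaths are censored. It follows because PD is the only event and everyone without PD is censored. If the death is a Grade 5 AE at least possibly related to treatment and arises on study therapy, Section 10.2 also counts it as unacceptable toxicity.

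**2. Direction**

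Suppose each death is censored at its own date. The PD-only and PD-or-death curves then have the same risk sets at every event time. At a PD both are multiplied by the same factor. At a death, with n patients at risk, the PD-or-death curve is multiplied by (1 - 1/n) and the PD-only curve by 1. The PD-only curve is therefore never below the other. This holds with other censoring present, provided it is applied identically to both.

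The direction is not guaranteed if last follow-up is read as the last scan, and Section 10.2 does not define it for a patient who has died. Take two responders: A has a last scan at month 1 and dies at month 4, and B has PD at month 3. Censoring A at month 1 leaves only B at risk at month 3, so the reported curve falls to 0. In truth 1 of 2, or 50%, are alive in response just after month 3.

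**3. Size**

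The plan gives no expected DOR, event count or precision target, so there is no figure of its own to reproduce. The input is f, the share of first post-response events that are deaths without PD. The documents do not give it, so a range is assumed.

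Under constant hazards, with true PD-or-death median M:

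- total hazard = ln 2 / M
- PD hazard = (1 - f) × ln 2 / M
- PD-only median = M / (1 - f)
- PD-only curve at time M = 0.5^(1 - f), where the true value is 50%

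| f (assumed) | Median multiplied by | PD-only curve at the true median | PD-only median if M is assumed to be 12 months |
|---|---|---|---|
| 0% | 1.00 | 50.0% | 12.0 |
| 5% | 1.05 | 51.8% | 12.6 |
| 10% | 1.11 | 53.6% | 13.3 |
| 20% | 1.25 | 57.4% | 15.0 |

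**The case against.** The case for leaving the text alone has four parts.

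- **Nothing is decided on DOR.** This stands. It is a secondary endpoint for preliminary estimation, with no test, threshold or sample size attached. Toxicity, ORR, CR rate, PFS and OS are unaffected, and the deaths still appear in PFS and OS.
- **Deaths in response may be rare.** This also stands, and the effect is zero if there are none. Section 9.2.6.1 asks for imaging on clinical suspicion of progression, and Section 9.5.3.4 seeks disease status until death. Section 4.4.5 reports one death (0.1%) from an adverse event of special interest on pembrolizumab alone, though in other tumours and not among responders specifically.
- **PD-only is stated openly and may be intended.** This stands in part. A careful reader can see the definition, but the plan does not label the measure as PD-only, and a PD-only measure still needs an estimator that allows for death.
- **Redefining an endpoint in an open-label trial with responses already known has a cost.** This stands and is dealt with in the fix.

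A reader might also infer more than the documents support:

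- **That every death without PD splits the two endpoints.** It does not, because outside lymphoma treatment censors both.
- **That every related fatal event is also unacceptable toxicity.** Section 10.2 limits that to events on study therapy, and responders may stop therapy after CR (Section 7.12.1).
- **That durability is a separate stated objective.** It belongs to the rationale. The objective in Section 3.2 lists DOR as one of several preliminary estimates.
- **That the durability of the 13 responders in Section 4.6.4 is overstated by a known amount.** That section says: "Among the initial 42 patients enrolled onto the study, there were 15 patients with prior exposure to PD-1 blockade". The 13 are the responders among those 15. They are not a planned DOR curve, since Section 11.1.3 says "These efficacy analyses will be performed separately for DLBCL, FL, and HL patients" and uses patients treated at the RP2D. The documents give no counts of PD or death among responders, so a worked example on 13 patients would rest on invented inputs.

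**Conclusion.** The point holds. As written, DOR and PFS handle death without PD differently, and Kaplan-Meier then treats that death as ordinary censoring. With deaths censored at their own date, the reported DOR is never shorter than time to PD or death. Under constant hazards the median is inflated by 1/(1-f), which is 5% to 25% for assumed f of 5% to 20% and nothing at f of 0%. These figures illustrate the mechanism and do not predict this trial's result.

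The change should be made because it is cheap and removes an ambiguity. It does not bear on the primary endpoint, the sample size or any decision rule.

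**What to change.** In Section 10.2:

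- Define DOR as the time from first CR or PR to PD or death from any cause, whichever comes first.
- Censor responders who are alive without PD at their last disease assessment. PFS also refers to last follow-up, so name the same date there.
- Keep the existing censoring at lymphoma treatment outside the protocol, as for PFS.

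If a PD-only measure is kept, label it as such, report the number of deaths in response, and estimate it as the cumulative incidence of PD with death as a competing event.

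Record that the change was made after responses in the first 42 patients were known.

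**Cost:** a short edit to the definitions. No new data are needed, because dates of death are already required for PFS and OS. Non-progression deaths on treatment and for up to 90 days after it are also reported expeditiously (Table 14.4).

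**Downsides:** the reported median DOR may be shorter, deaths unrelated to lymphoma will count as events, and the definition changes with response data in hand.

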9.5.3.4 Follow-up Visits

Subjects who discontinue trial treatment for a reason other than disease progression will move into the Follow-Up Phase and should be assessed every 12 weeks (84 ± 7 days) by radiologic imaging to monitor disease status. After 1 year, the imaging time point will occur every 18 weeks (± 7 days). Every effort should be made to collect information regarding disease status until the start of new anti-neoplastic therapy, disease progression, death, and end of the study. Information regarding post-study anti-neoplastic treatment will be collected if new treatment is initiated.

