10.0 ENDPOINT EVALUATION CRITERIA/MEASUREMENT OF EFFECT

10.1 Response Criteria

Disease response/progression will be evaluated using 2014 Lugano Classification (see Appendix C)^{122, 139}. Participants who meet the definition of progressive disease per Lugano Classification should be evaluated using the LYRIC criteria (see Appendix L).

For all patients:

- Disease staging will be performed every 4 cycles until disease progression or off study therapy.
- Disease assessment will be performed either by PET-CT (FDG-avid histologies) or diagnostic quality CT of the neck, chest, abdomen and pelvis (N/C/A/P) with IV contrast (see restrictions below).
- MRI may be performed at the investigator's discretion for lesions not well-visualized by CT, or if CT with intravenous contrast is contraindicated.
- Whenever a PET-CT is not performed, a diagnostic quality (N/C/A/P) CT with IV contrast must be performed instead.

Note: if there is no evidence of neck involvement by lymphoma at baseline, CT of chest, abdomen and pelvis (C/A/P) can be performed instead of N/C/A/P at subsequent re-staging.

For DLBCL and HL patients only:

- Disease assessment requires a PET-CT be performed at baseline (within the screening window) and at cycle 4 (Day 15-21 [-3 days]).
- Although not required, it is recommended that DLBCL and HL patients who are not in CR get a PET-CT at least every 8 cycles thereafter, and every 24 weeks for patients who discontinued for other reasons than CR.
- Assessment with PET-CT is required to confirm CR. Once CR has been confirmed, diagnostic quality (N/C/A/P) CT with IV contrast can be used instead of PET-CT until progression, unless otherwise specified below.
Note: if there is no evidence of neck involvement by lymphoma at baseline, CT of chest, abdomen and pelvis (C/A/P) can be performed instead of N/C/A/P at subsequent re-staging.

For FL patients only:

- Disease assessment by diagnostic quality (N/C/A/P) CT with IV contrast or PET-CT is allowed at any time point.
Note: if there is no evidence of neck involvement by lymphoma at baseline, CT of chest, abdomen and pelvis (C/A/P) can be performed instead of N/C/A/P at subsequent re-staging.

PET-CT and CT results will be read by radiology at each study site and investigator response based on radiology reading will be performed. Lymphoma response assessment based on PET-CT/CT will be based on the 2014 Lugano Classification (Appendix C).¹³⁹

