17.5 Participant Withdrawal

Participants may withdraw from the study at any time and for any reason without prejudice. The withdrawal must be documented per institutional policies.

Participant withdrawal may consist of any of the following with regard to study procedures and data collection:

- Withdrawal from study treatment, but agreement to continue with active study procedures and chart review and follow-up procedures.
- Withdrawal from study treatment and all active procedures, but agreement for chart review and follow-up procedures.
- Withdrawal from study treatment, all active procedures, and any future data collection.

Participants who agreed to the collection of research blood samples may withdraw consent to use their specimens, if they are not yet processed as detailed in the consent form. Once the PI and site PI is notified of this withdrawal of informed consent, the research specimens will not be used in any research. At that time, any of the existing specimens will be destroyed.

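### PFS and DOR are censored at an undefined last follow-up, not at the last disease assessment, so unscanned time can count as progression-free

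*Combined protocol and SAP*

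**What the plan says.** Section 10.2 (Endpoint Definitions) has three parallel rules for patients without an event.

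- PFS: "If the patient has not progressed relapsed or died, the patient is censored at the time of last follow-up".
- DOR: "Patient who has not had disease progression/relapse at last follow-up is censored at the time of last follow-up".
- OS: "If a patient is alive at the last evaluation time period, survival time is censored at the time of last follow-up".

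The shared term is not defined. Neither Section 10.2 nor Section 11.1.3 links the PFS or DOR censoring date to a disease assessment, and neither has a rule for missed scans. For a switch of therapy, PFS and DOR share this sentence: "If a patient receives non-protocol anti-lymphoma treatment prior to disease progression, the patient is censored at the time of non-protocol anti-lymphoma treatment".

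On imaging, Section 10.1 says: "Disease staging will be performed every 4 cycles until disease progression or off study therapy". Under Section 9.5.3.4, patients who stop treatment without progression "should be assessed every 12 weeks (84 ± 7 days) by radiologic imaging to monitor disease status"; after one year the interval becomes 18 weeks. Footnote k of the study calendar (Section 8.1) limits the discontinuation scan to patients who stop for progression.

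Section 17.5 lists this among the permitted forms of withdrawal: "Withdrawal from study treatment and all active procedures, but agreement for chart review and follow-up procedures". Section 11.1.3 estimates PFS and DOR by Kaplan-Meier, separately for DLBCL, FL and HL.

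**The concern.** A Kaplan-Meier risk set should hold only patients in whom the event could have been observed. A patient who has given up scans but is still followed through the chart is alive and in contact, which is enough for OS. It is not enough for an endpoint detected mainly by imaging. If that patient stays at risk until the last chart entry, any progression that nobody recorded is counted as progression-free time.

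When the error is not zero it raises the curve, and a single-arm trial has no control arm to share it. The histology groups are small parts of about 52 patients and DOR uses responders only, so a few such patients could affect the later part of a curve. PFS also feeds the biomarker and quantitative PET analyses in Section 11.4.

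**Working it through.** **Plan's own figure.** The documents state no PFS or DOR median, event count or power, so there is nothing to reproduce. The only related number is the sample size in Section 11.3: 12 + 40 = 52.

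**Scan interval.** On treatment: 4 cycles × 21 days = 84 days = 12 weeks. Off treatment: 12 weeks in the first year, then 18 weeks.

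**Mechanism.** At a scan date with d progressions among r patients still being scanned, the survival factor should be 1 − d/r. If u unscanned patients are also held at risk, it becomes 1 − d/(r + u), which is larger whenever u > 0 and d > 0. With u = 0 the two agree.

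**Base simulation.** There were 4,000 patients per setting, with scans every 12 weeks to about 24 months and every 18 weeks after that. Assumptions not in the documents:

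- exponential time to progression, median 26 or 52 weeks;
- last contact uniform over weeks 52-156;
- a fraction of patients stops imaging at a time uniform over weeks 6-78, independently of progression, and stays in contact;
- no later progression is recorded;
- no deaths.

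As a check on the complete-imaging column, the last scan before week 52 is at week 48, so the expected values are 0.5^(48/26) = 27.8% and 0.5^(48/52) = 52.7%. The simulated values scatter around these.

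52-week PFS:

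| Median (weeks) | Stop imaging | Complete imaging | Censor at last follow-up | Censor at last scan | Inflation (points) |
|---|---|---|---|---|---|
| 26 | 0% | 26.7% | 26.7% | 26.7% | 0 |
| 26 | 10% | 28.4% | 30.4% | 28.4% | 30.4 − 28.4 = 2.0 |
| 26 | 20% | 28.6% | 32.4% | 28.8% | 32.4 − 28.6 = 3.8 |
| 52 | 0% | 52.8% | 52.8% | 52.8% | 0 |
| 52 | 10% | 52.2% | 53.3% | 52.0% | 53.3 − 52.2 = 1.1 |
| 52 | 20% | 53.4% | 56.4% | 53.6% | 56.4 − 53.4 = 3.0 |

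In this table, censoring at the last scan stays within 0.2 points of complete imaging.

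**Sensitivity.** Inflation of 52-week PFS in points, for 10% / 20% stopping:

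| When imaging stops | Later progressions found in the chart | Median 26 weeks | Median 52 weeks |
|---|---|---|---|
| Early (exponential, mean 26 weeks) | none | about 4 / 8 | about 3 / 6 |
| Early | 50% | about 2 / 5 | about 2 / 3 |
| Early | 80%, mean lag 13 weeks | about 1.5 / 2.7 | about 1 / 2 |
| Later (uniform, weeks 6-78) | none | 2.0 / 3.8 | 1.1 / 3.0 |

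Later stopping, with or without chart detection, spans about 0.5 to 4 points. Over all settings the range is roughly 0.5 to 8 points.

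**What the reference is.** Inflation is measured against complete scheduled imaging, not against the true time of progression. With an exponential median of 39 weeks the true 52-week value is 0.5^(52/39) = 0.397, while complete scanning every 12-14 weeks gives about 0.450. That gap of about 5 points comes from finding progression only at scans, and a new censoring date does not remove it.

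**The case against.** The strongest reply has four parts.

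1. *Last follow-up may mean the last follow-up visit.* Under Section 9.5.3.4 that is an imaging visit. This reading is possible, but the plan does not state it. It would also give one term two meanings inside Section 10.2, because OS follow-up (Section 9.5.3.4.1) runs by record review, registry or telephone.

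2. *Chart review can find progression.* PFS counts the first observed relapse, progression or death and is not limited to protocol scans. New therapy also ends the credited time, and Section 9.5.3.4 asks for continued effort to learn disease status. This stands. It reduces the effect, as the sensitivity table shows, but removes it only if every later progression is recorded promptly.

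3. *Patients who keep to the schedule cause no bias.* This also stands. A reader might infer that PFS and DOR are overstated as a matter of course, by 4 or 8 points. The documents do not support that: they give no rate or timing of imaging withdrawal, and those figures need early stopping with no later progression ever recorded.

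4. *The consequence is small.* PFS and DOR are secondary, preliminary estimates with no test or threshold. At a PFS of 0.45, even with all 52 patients, the standard error is √(0.45 × 0.55 / 52) = 0.069, about 7 points. A reader might also infer that a planned comparison with historical PFS is compromised. No such comparison is specified; the improvement discussed in Section 4.6.5.2 concerns ORR and CR rate. This limits the weight of the point, but it does not justify counting unobserved time as progression-free.

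**Conclusion.** The point holds in conditional form. As written, Section 10.2 permits PFS and DOR to be censored after the last scan, and Section 17.5 creates patients for whom that gap can be long. The estimates may then be overstated; they are not shown to be.

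The inflation of 1-year PFS is zero with full adherence to the scan schedule. It is roughly 0.5 to 8 points if 10-20% stop imaging but remain in contact. The range rests on assumed stopping rates, stopping times, chart detection and exponential progression. The base simulation also assumes that stopping is unrelated to progression risk; if it is related, censoring at the last scan would not be unbiased either. No stated figure and no decision rule in the plan changes.

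**What to change.** In Section 10.2, censor event-free patients for PFS and DOR at the date of the last evaluable disease assessment without progression. For patients who start non-protocol anti-lymphoma therapy before progression, use the last such assessment on or before its start. Keep last contact as the censoring date for OS only. The definition should also say whether a standard-of-care scan, or a progression documented only in the chart, counts as an assessment or an event.

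The change is to wording. Response assessment forms are already collected (Section 15.3), and no patient procedure changes. The downside is slightly shorter follow-up for PFS and DOR and possibly less favourable estimates.

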11.2 Safety Analysis and Stopping Rules for Excessive Toxicity in the Expansion Cohort

During enrollment into the expansion cohort, toxicity information recorded will include the type, severity, and the probable association with the study regimen. Tables will be constructed to summarize the observed incidence by severity and type of toxicity.

Because of the unique immune-related adverse events (IrAEs) observed with checkpoint inhibitors, we will monitor for “unacceptable toxicity” with this new combination of drugs

(defined in [Section 10.2](#)). The expected rate of “unacceptable toxicity” should not be $\geq 33\%$. The early stopping rule for unacceptable toxicity will be assessed after enrollment of 12 patients (total, across cohorts) treated at the RP2D and will be assessed once the 12th patient has completed at least 4 cycles of therapy. If >3 “unacceptable toxicity” events occur in the first 12 patients ($\geq 33\%$) treated (across disease subtypes) at RP2D, or at a rate $\geq 33\%$ anytime thereafter at the quarterly review, accrual will be halted and a full review of these events will be performed by the City of Hope Data Safety Monitoring Committee (DSMC). Patient accrual will not resume until approved by the DSMC to do so. These rules are in addition to the quarterly review of all toxicities submitted to the City of Hope Data Safety Monitoring Committee (DSMC). Patients with ongoing toxicity will be followed until resolution or stability.

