14.2.3 Abnormal Liver Function Tests

An elevated AST or ALT lab value that is greater than or equal to 3X the upper limit of normal and an elevated total bilirubin lab value that is greater than or equal to 2X the upper limit of normal and, at the same time, an alkaline phosphatase lab value that is less than 2X the upper limit of normal, as determined by way of protocol-specified laboratory testing or unscheduled laboratory testing.

These criteria are based upon available regulatory guidance documents. The purpose of the criteria is to specify a threshold of abnormal hepatic tests that may require an additional evaluation for an underlying etiology.

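### The 'or' in the hepatitis exception to unacceptable toxicity, read literally, keeps a persistent Grade 3 hepatitis confined to transaminases (or to bilirubin) out of the count that halts accrual

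*Combined protocol and SAP*

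**What the plan says.** Section 10.2 defines unacceptable toxicity through three limbs, each requiring at least a possible relation to study treatment.

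- The first is "Any Gr 3 or higher IrAE that does not resolve to Gr ≤ 1 within 7 days with the exception of" three listed items. The liver item is "Grade 3 immune-related hepatitis if ALT or AST $< 8 \times$ ULN or total bilirubin $< 5 \times$ ULN".
- The second is "Any other Gr ≥ 4 AE with the exception of" laboratory findings without clinical significance and local inflammatory responses.
- The third is any Grade 5 event.

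Section 11.2 uses this definition as a halting rule: "The expected rate of “unacceptable toxicity” should not be" 33% or more. If more than 3 "events occur in the first 12 patients" treated at the RP2D, or the rate is 33% or more at a later quarterly review, "accrual will be halted and a full review of these events will be performed" by the DSMC. Section 7.5 and the synopsis in Section 1.0 carry the same thresholds.

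Two other places set liver criteria. Section 14.2.3, on expedited reporting, joins its limits with 'and': "An elevated AST or ALT lab value that is greater than or equal to 3X the upper limit of normal and an elevated total bilirubin" of at least 2 x ULN, with alkaline phosphatase below 2 x ULN. The hepatic row of Table 5 is entered on AST/ALT or on bilirubin, and its action at Grade 3 or 4 is permanent discontinuation of pembrolizumab.

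**The concern.** An exception that lists limits would normally spare the milder cases and count the rest. Here the limits are joined by 'or', so an event is spared as soon as any one value is under its limit. Take a Grade 3 case lasting more than 7 days with ALT 15 x ULN, AST 12 x ULN and normal bilirubin. Both transaminases are well past the 8 x limit, yet the event is excepted because bilirubin is below 5 x.

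This matters because unacceptable toxicity is the only numeric safety trigger in the expansion, and the plan says it was set up because of immune-related events. With 12 patients, one case can decide the outcome: 4/12 halts accrual and 3/12 does not. The reported rate of unacceptable toxicity would carry the same downward error.

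**Working it through.** **Step 1. The plan's own boundary.** More than 3 of 12 means at least 4, and 4/12 = 33.3%, while 3/12 = 25%. The count and the 33% agree. The plan gives no operating characteristics for the rule.

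**Step 2. What the wording counts.** Mark ALT, AST and total bilirubin as under, or at or above, their limits (8 x, 8 x, 5 x). That gives 2 x 2 x 2 = 8 patterns for a Grade 3 immune hepatitis lasting more than 7 days.

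| Reading of the exception | Event counts when | Patterns counted |
|---|---|---|
| Literal: any one value under its limit excuses | ALT, AST and bilirubin all at or above | 1 of 8 |
| 'ALT or AST < 8' taken to mean both under 8, then 'or' bilirubin | either transaminase and bilirubin at or above | 3 of 8 |
| All values must be under their limits to be excused | any value at or above | 7 of 8 |

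The pattern counts describe logic; they are not frequencies of patients. On both 'or' readings an event needs bilirubin at or above 5 x to count, so a transaminase-only case never counts. A bilirubin-only case never counts either. The 8 x limit has no effect by itself.

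**Step 3. Does another limb bring the event back?** No. The second limb starts at Grade 4 and the third is Grade 5.

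**Step 4. Size when hepatitis is rare.** Section 4.4.5 gives serious drug-related hepatitis as 0.7% on pembrolizumab alone; use it here as a stand-in for persistent Grade 3 hepatitis. Assume other unacceptable toxicity at 20%, half of the hepatitis cases with transaminases at or above 8 x, one in ten with bilirubin at or above 5 x, and independence. None of these four is in the documents. The share counted is 0.5 x 0.1 = 0.05 under 'or', and 1 - 0.5 x 0.9 = 0.55 when all values must be under their limits. With X binomial, n = 12:

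- 'or': rate 0.20 + 0.007 x 0.05 = 0.20035, P(X >= 4) = 0.206
- all limits required: 0.20 + 0.007 x 0.55 = 0.20385, P = 0.216
- every such hepatitis counted: 0.207, P = 0.224

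The differences are 0.216 - 0.206 = 0.010 and 0.224 - 0.206 = 0.018.

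**Step 5. Size if the combination raises it.** Let the true rate be 33.3%, of which 5 or 10 percentage points are events that the 'or' excuses (assumed, for illustration).

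| Points excused | Counted rate | P(X >= 4 of 12) |
|---|---|---|
| 0 | 0.333 | 0.607 |
| 5 | 0.283 | 0.456 |
| 10 | 0.233 | 0.300 |

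**Step 6. Which look is still ahead.** Section 4.6.4 reports on the first 42 patients enrolled and plans 10 more. With 12 expected in escalation, 42 - 12 = 30 would already be in the expansion, so the 12-patient look is probably past. The trigger still running is the rate of 33% or more at quarterly review, to which the same definition applies.

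**The case against.** The strongest reply is that the sentence was meant analyte by analyte: a transaminase event is judged against 8 x and a bilirubin event against 5 x. Table 5 enters its hepatic row on either analyte, which fits that style. The reading is plausible, but it does not rescue the text. Under it the case with ALT 15 x counts, whereas the literal text excuses it. That leaves a halting endpoint on which two careful reviewers can disagree about the same patient.

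A reader might infer that almost every persistent Grade 3 hepatitis is excluded. The documents do not support that. It needs the share of such cases with bilirubin at or above 5 x ULN, which is nowhere given.

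A reader might also infer that Section 10.2 contradicts Table 5 and Section 14.2.3. Table 5 governs one patient's drug. Section 14.2.3 says its purpose is to "specify a threshold of abnormal hepatic tests that may require an additional evaluation for an underlying etiology". A halting definition may be narrower than either. What stands is that an event that ends pembrolizumab under Table 5 can be missing from the count, and that Section 14.2.3 shows the protocol using 'and' where it wants limits to hold jointly.

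The safeguards are real. The exception covers Grade 3 only, so persistent Grade 4 and all Grade 5 hepatitis still count. The DSMC reviews all toxicities quarterly in addition to this rule, the liver abnormalities of Section 14.2.3 are reported expeditiously, and toxicity is summarised by type and severity regardless. These limit the harm, but none of them is a numeric trigger.

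Finally, hepatitis is rare on pembrolizumab alone, and Step 4 shows how little the wording then matters. But Section 4.6.3 itself names overlapping toxicity and potentiation of immune effects as reasons for dose escalation, and the halting rule is there to catch such an increase.

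**Conclusion.** The point holds as a wording defect in a halting endpoint. Taken literally, Section 10.2 never counts a persistent Grade 3 immune hepatitis confined to transaminases or to bilirubin, and its 8 x limit never acts alone. That conclusion follows from the text and needs no assumption. The direction is also certain: compared with requiring every value to be under its limit, the literal 'or' can only lower the count.

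The size is not certain. At the documented monotherapy rate the chance of halting at 12 patients moves by about 0.01 to 0.02, given the assumptions in Step 4. The falls from 0.61 to 0.46 or 0.30 rest on an assumed 5 or 10 points of excused hepatitis. A reader might take the latter figures as a forecast that a halt was or will be missed. The documents give no hepatitis rate for the combination, and the 12-patient look is probably past, so they do not show that. What remains exposed is the quarterly review and the reported rate.

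**What to change.** For the halting count (Sections 11.2 and 7.5 and the synopsis) and the reported rate of unacceptable toxicity only:

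1. Restate the exception so that each of the sponsor's existing limits operates: a persistent Grade 3 immune hepatitis is excepted only when ALT, AST and total bilirubin are all under their stated limits.
2. Say explicitly whether ALT/AST means either or both.
3. Re-adjudicate the liver immune-related events already recorded at the RP2D under the restated wording, and carry the result into the ongoing quarterly review.

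The cost is one line of text and a re-check of laboratory values already held. The observed rate may rise slightly.

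Sections 7.1.1 and 7.12 use the same definition to end treatment, and Table 5 has its own rule for Grade 3 or 4 hepatic events. Changing the shared sentence would change that use too, so the sponsor must reconcile those passages separately. No clinical rule is proposed here.
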